Although newer treatments such as intravitreal anti-angiogenic drugs have shown slightly better visual outcomes than PRP, the latter remains essential. Studies suggest that combining these drugs with PRP is as effective and offers additional benefits, such as lower costs and fewer required ophthalmic visits and injections, thereby improving treatment adherence.^{14–16} However, PRP is often painful, with studies reporting pain in more than 70% of patients.¹⁷ This discomfort can result in the application of fewer burns and suboptimal treatment, increasing the risk of vision loss.^{18,19} Thus, effective pain management during PRP is critical for reducing patient discomfort, therefore improving patient adherence and treatment efficacy. Topical anesthetics, such as lidocaine and tetracaine, are commonly used in ophthalmic procedures but often provide insufficient pain relief during PRP.^{20,21} Studies have shown that regional interventions, such as peribulbar injections or the combination of topical anesthesia with subconjunctival injections, reduce pain perception and improve procedural outcomes.^{17,22-23}

Among invasive anesthesia techniques, retrobulbar blocks are highly effective due to their rapid onset and complete akinesia and analgesia,^{24,25} but they carry risks such as retrobulbar hemorrhage, optic nerve injury, and cardiorespiratory complications.^{24,26} Peribulbar anesthesia offers similar efficacy by leveraging communication between the extraconal and intraconal spaces while reducing the risk of serious complications such as globe perforation.²⁷ Our anesthetic approach combines short-acting lidocaine with long-acting bupivacaine, optimizing both rapid onset and prolonged analgesia.²⁵ Although many studies have evaluated less invasive strategies such as topical or oral analgesics, their effectiveness in PRP pain management has been limited. A meta-analysis by Arruda et al.²¹ of 15 randomized controlled trials and four crossover trials found that only peribulbar 2% lidocaine significantly reduced pain compared with placebo. Other interventions, including NSAIDs, topical anesthetics, pregabalin, opioids, and acetaminophen, did not yield statistically significant results. Additional studies comparing peribulbar anesthesia with topical agents confirmed superior pain control, particularly during the PRP session, though not at the 48-hour follow-up.²⁸ Subconjunctival lidocaine has also demonstrated efficacy in lowering pain scores, reducing session duration, and increasing the number of laser burns applied.^{22,23} However, more research is needed to compare this technique to peribulbar anesthesia directly.

Despite supporting evidence for several anesthetic approaches, the pain measurements in these studies were predominantly subjective. Pain perception is influenced by various factors—genetic, psychological, cultural, and social²⁹—making objective indicators a valuable complement. Sympathetic responses to pain, such as changes in heart rate, respiratory rate, blood pressure, and oxygen saturation, provide measurable markers.³⁰ Wu et al.¹⁷ compared different anesthetic techniques and found that only peribulbar 2% lidocaine significantly lowered pain scores compared with the control group.

This study aimed to evaluate the efficacy of peribulbar anesthesia using 2% lidocaine and 0.5% bupivacaine compared with topical 5% tetracaine in reducing pain during laser PRP in patients with PDR, using pain rating as a subjective parameter and vital signs as objective parameters.

Research question

What is the analgesic effect of peribulbar anesthesia compared to topical anesthesia in patients with diabetic retinopathy undergoing PRP with argon laser?

Objectives and hypotheses

General objective

To determine the reduction in the NRS scale between eyes of patients undergoing PRP following an injection of peribulbar anesthesia with 2% lidocaine + 0.5% bupivacaine versus those eyes receiving a sham injection.

Specific objectives

- To determine the pain score using the NRS scale between the eyes of patients undergoing PRP following the application of a sham injection vs transeptal anesthesia with 2% lidocaine + 0.5% bupivacaine.
- To measure and compare the frequency of adverse effects and complications associated with the transeptal anesthesia intervention versus those of patients receiving a sham injection.
- To measure heart rate before and after the application of panretinal photocoagulation.
- To measure respiratory rate before and after the application of panretinal photocoagulation.

-
- To measure systolic and diastolic blood pressure pre- and post-application of panretinal photocoagulation.
- To measure oxygen saturation pre- and post-application of panretinal photocoagulation.

General hypothesis

In patients who received panretinal photocoagulation, eyes undergoing peribulbar anesthesia will present a lower pain score on the NRS scale than eyes that received a sham injection.

Specific hypotheses

- In patients who received panretinal photocoagulation, eyes undergoing peribulbar anesthesia will present a pain score on the NRS scale 20% lower than eyes that only received a sham injection.
- The incidence of adverse effects and complications of peribulbar anesthesia is similar to that of the sham injection.
- In eyes undergoing intervention with prior peribulbar anesthesia, the post-procedure increase in heart rate will be 10% lower than the increase observed in eyes receiving a sham injection.
- In eyes undergoing intervention with prior peribulbar anesthesia, the post-procedure increase in respiratory rate will be 10% lower than the increase observed in eyes receiving a sham injection.

- In eyes undergoing intervention with prior peribulbar anesthesia, the post-procedure increase in systolic and diastolic blood pressure will be 10% lower than the increase observed in eyes receiving a sham injection.

Methods

Study design

Prospective, randomized, single-masked, controlled trial

Patients

Patients were recruited from the Asociación Para Evitar la Ceguera en México, I.A.P. Retina department according to specific eligibility criteria. Adults aged 18 years or older with proliferative diabetic retinopathy who were scheduled to undergo their first PRP session and were able to maintain the required posture at the slit lamp throughout the procedure were included. Exclusion criteria were a history of phobic anxiety disorder related to needles or injections; known allergies or hypersensitivity to lidocaine, bupivacaine, or tetracaine; use of analgesics within 24 hours prior to treatment; and cognitive or motor impairments that could hinder effective communication of pain.

Study design

A block randomization scheme was created to ensure a balanced allocation of the eyes across the study groups. Eleven blocks containing four possible permutations for the two groups were created. The intervention group received peribulbar anesthesia and the control group received topical anesthesia. The blocks were numbered randomly from one to 11, and one eye of each participant was assigned to the treatment or control group according to the permutation, with the contralateral eye assigned to the corresponding alternative.

The eyes assigned to the treatment group received a single drop of topical 5% tetracaine to improve patient comfort during the peribulbar injection, followed by a two-minute observation period. A mixture of 1.5 mL of 0.5% bupivacaine and 1.5 mL of 2% lidocaine was prepared in a 3 mL syringe. The peribulbar injection was administered using a 25G needle inserted horizontally through the inferior palpebral conjunctiva, directed axially over the infraorbital rim, and then angled upward to deliver the anesthetic into the orbit.

After a five-minute latency period, the eyes assigned to the control group, which also received 5% tetracaine, were administered a sham injection. In this group, topical 5% tetracaine was applied, followed by a two-minute observation period. The sham injection consisted of a 3 mL syringe filled with normal saline, without a needle, used to simulate insertion by applying pressure at the same site as the peribulbar injection.

Five minutes after the sham injection, the participants underwent PRP using a double-frequency Nd:YAG 532-nm laser (PUREPOINT®, ALCON) following the standard PRP protocol, starting with the right eye. Each eye received between 1,200 and 1,500 burns, with sizes ranging from 200 μ m to 500 μ m. Pulse durations were set between 100-200 ms. The power was titrated before initiating treatment to obtain a gray-whitish burn, and adjusted throughout the procedure in order to avoid under- or over-treatment. A period of 10 minutes was provided between the right- and left-eye PRP sessions.

Variables and Measurements

The primary variable assessed in this study was patient perception of pain during PRP administration in each eye, measured using the numerical rating scale (NRS). The Initiative on Methods, Measurement, and Pain Assessment in Clinical Trials (IMMPACT) recommends the use of this scale due to its simplicity, patient preference, and high completion rates, especially among elderly individuals. The NRS measures pain intensity on a scale of 0 to 10, where 0 corresponds to the absence of pain and 10 represents the

worst pain imaginable.²⁴ The evaluator administering the NRS was not masked to the treatment allocation. The secondary variables assessed in this study were heart rate, respiratory rate, oxygen saturation (SpO₂), and blood pressure measured before and after the application of PRP in each eye. All vital signs were measured with the Aquarius Vital Sign Monitor (Shenzhen Northern Meditec Limited, Shenzhen, China) at baseline before the start of PRP, and at the 1-, 5-, 10-, and 15-minute marks while undergoing PRP application in each eye.

Safety was evaluated by monitoring for ocular and non-ocular adverse events, assessing extraocular movements after peribulbar injection, and conducting a 45-minute observation period after the PRP session.

Standardized methods

A) Topical anesthesia with 0.5% Tetracaine

1. Patient seated in a comfortable position.
2. 1 drop of 0.5% tetracaine will be applied onto the ocular surface to be treated and the conjunctival fornices.
3. Any excess residue will be cleaned with a cotton swab.

B) Peribulbar injection of 3 mL of 2% lidocaine + 0.5% bupivacaine

1. Patient in a comfortable position.
2. 2 drops of 0.5% tetracaine will be applied to the conjunctival fornices 10 minutes prior to the administration of anesthesia.
3. A Mixture of 1.5 mL of 2% lidocaine and 1.5 mL of 0.5% bupivacaine will be prepared in a 5 mL syringe.
4. Lower eyelid skin will be cleaned with 97% alcohol.

5. Palpation of the orbital notch with the index finger or thumb, located at the junction of the outer 1/3 and the inner 2/3 of the orbital rim.
6. The patient will be asked to look upward (supraversion).
7. Using a 5 mL syringe, a 25G needle will be inserted, bevel up, through the skin, entering near the bony margin, lateral to the notch.
8. Aspiration prior to injecting the medication will be performed.
9. 3 mL of 2% lidocaine + 0.5% bupivacaine will be injected
10. Extraocular movements will be evaluated.

Sham peribulbar injection

1. Patient in a comfortable position.
2. 2 drops of 0.5% tetracaine will be applied to the conjunctival fornices 10 minutes prior to the administration of anesthesia.
3. Lower eyelid skin will be cleaned with 97% alcohol.
4. Palpation of the orbital notch with the index finger or thumb, located at the junction of the outer 1/3 and the inner 2/3 of the orbital rim.
5. With a 5 ml syringe filled with normal saline without a needle, a peribulbar injection will be simulated near the bony margin, lateral to the notch.
6. Extraocular movements will be evaluated.

Statistical Analysis Plan

The sample size was calculated using a two-sample t-test to compare two means, based on previous results reported by Zakrzewski et al.³¹ Assuming an alpha risk of 0.05 and a beta risk of 0.2, a minimum of 44 patients was required to find statistically significant differences. The Shapiro-Wilk test was used to assess normality. Descriptive statistics were used to analyze the baseline population characteristics. Data from normally distributed variables is

presented as mean (SD), and data from non-normally distributed variables as median (IQR). The grouped quantitative variables had a normal distribution; however, when the treatment groups were separated, all the variables had a non-normal distribution. Repeated measurements of related groups with a non-normal distribution were analyzed using the Friedman test. Group comparisons of unrelated groups with a non-normal distribution were performed using the Mann-Whitney U test. The measurements of vital signs, NRS score, and laser parameters were registered into a coded Excel spreadsheet (Microsoft Corporation), and statistical analysis was performed using SPSS software (version 29.0, IBM, Chicago, IL, USA). A p-value of < 0.05 was considered statistically significant.

References

6. GBD 2019 Blindness and Vision Impairment Collaborators. Causes of blindness and vision impairment in 2020 and trends over 30 years, and prevalence of avoidable blindness in relation to VISION 2020: the Right to Sight: an analysis for the Global Burden of Disease Study. *Lancet Glob Health.* 2021;9(2):e144-e160. doi:10.1016/S2214-109X(20)30489-7

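### For non-ocular adverse events after the sham there is no drug-free comparator, because every patient has both the block and the sham before any laser

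*Combined protocol and SAP*

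**What the plan says.** Under Specific objectives, the plan sets out to compare "complications associated with the transeptal anesthesia intervention versus those of patients receiving a sham injection". Under Specific hypotheses it expects that "The incidence of adverse effects and complications of peribulbar anesthesia is similar to that of the sham injection". No margin or expected rate is attached to that statement.

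The second Study design section of Methods randomises one eye of each participant, "with the contralateral eye assigned to the corresponding alternative". The block comes first. The text continues: "After a five-minute latency period, the eyes assigned to the control group, which also received 5% tetracaine, were administered a sham injection". The sham is a saline-filled syringe "without a needle, used to simulate insertion by applying pressure at the same site as the peribulbar injection". Then, "Five minutes after the sham injection, the participants underwent PRP", right eye first. "A period of 10 minutes was provided between the right- and left-eye PRP sessions".

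Under Variables and Measurements, "Safety was evaluated by monitoring for ocular and non-ocular adverse events", together with a check of eye movements and one 45-minute observation once PRP is finished. The Statistical Analysis Plan does not mention adverse events. It gives no test, no unit of count (eye or patient) and no rule for attributing an event to an arm.

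**The concern.** The objective is worded as if one set of patients had the block and another had the sham. In this design they are the same people. Pain can be scored for each eye in turn and an ocular complication can be seen in one eye, but a non-ocular event belongs to the whole patient. Once both procedures have been given, the patient carries the injected lidocaine and bupivacaine whichever eye is being treated.

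The hypothesis predicts similarity, so any rule that moves block-related events into the sham arm favours the expected answer. A reader of the results could take similar non-ocular event rates as evidence that the block adds no systemic risk, when the comparison had no means of showing otherwise.

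**Working it through.** **Plan's own figure.** The plan states no figure for safety. The 44 patients in the Statistical Analysis Plan come from the pain comparison. That number cannot be reproduced, because its difference and SD are not given. It serves below only as the number of patients.

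**Sequence of exposure** (second Study design section, and its continuation before Variables and Measurements)

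1. Block in the assigned eye: time 0.
2. Sham in the other eye: after a 5-minute latency.
3. Laser to the right eye: 5 minutes after the sham, so at least 5 + 5 = 10 minutes after the block.
4. A 10-minute gap, then laser to the left eye.
5. One 45-minute observation for the patient.

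A patient has had the block without the sham between steps 1 and 2. At no time has a patient had the sham without the block. A drug-free sham rate for non-ocular events is therefore never observed.

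**What each counting rule gives for non-ocular events after the sham.** The plan does not choose among these.

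- *Per patient, under both arms.* With k affected patients, the rates are k/44 and k/44. The difference is k/44 − k/44 = 0, with no discordant pairs. Fisher's exact p is 1 for k = 0, 1, 5 and 10. The true risk of the block drops out.
- *By the eye under laser.* Suppose m block-caused events occur during laser, a fraction s of them while the sham eye is treated. The block arm receives (1 − s)m and the sham arm sm. The observed difference is (1 − 2s)m/44, whereas the block-caused excess is m/44. The documents say nothing about s. Over s = 0 to 1 the observed difference runs from +m/44 to −m/44, and it is right only at s = 0. Events before the first laser, in the gap between eyes or during the final observation have no eye under laser and so no arm.
- *By causal judgement.* Toxicity from the injected anesthetics would go to the block. The sham rate for such events is then zero by definition, not by observation. Non-specific events, such as a vasovagal reaction during laser, remain ambiguous. The plan does not say who judges, or whether they are masked.
- *Once per patient.* This gives one incidence after peribulbar exposure, which the design can estimate. With 0 events in 44, the exact two-sided 95% upper limit is 1 − 0.025^(1/44) = 0.080, or 8.0%.

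**Ocular events.** These can be assigned to an eye and compared within pairs. With k block-only and no sham-only events, the exact two-sided McNemar p is 2 × 0.5^k: 0.0625 for k = 5 and 0.031 for k = 6. At least 6/44 = 13.6% against 0% is therefore needed. Assuming no sham events, the chance of 6 or more is:

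| Assumed block rate | Power, 44 pairs |
|---|---|
| 5% | 2.2% |
| 10% | 27% |
| 15% | 66% |
| 20% | 90% |

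A 2% block complication has a 0.98^44 = 41% chance of not appearing at all. A non-significant ocular result would not show similarity either.

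**The case against.** The strongest reply is that the plan never says events are counted in both arms. Most other comparisons under Specific objectives and Specific hypotheses are worded by eye, so the reference to patients may only be loose drafting. Onset time helps, since an event before the sham can only follow the block. Mechanism helps too, since needle-free saline cannot cause lidocaine or bupivacaine toxicity. Shared systemic exposure is inherent in any fellow-eye design. This is a secondary objective with no test in the Statistical Analysis Plan, and the primary pain result does not depend on it.

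Most of this stands, and it limits the point. A reader might infer that the whole safety comparison must come out similar by construction, or that no non-ocular event can be assigned to an arm. The documents support neither. The zero difference needs a double-counting rule that they do not state. The window between block and sham allows attribution by time. Ocular complications can differ between eyes, all the more because the sham uses no needle.

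The reply does not supply a comparator. Correcting the wording to eyes does not create sham-only exposure. Timing and mechanism can place some events with the block but cannot produce a drug-free sham rate for the rest. The fact that such exposure is inherent in the design is a reason not to state a between-arm hypothesis about non-ocular events.

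**Conclusion.** The point holds for non-ocular events arising after the sham. For these, the stated objective and hypothesis claim a between-arm contrast that the design cannot deliver, and all 44 of 44 patients are affected. The size of the distortion depends on a counting rule the plan omits. The difference is exactly zero if events are counted per patient under both arms. If events follow the eye under laser, the distortion is of unknown size, because no document gives the share that would fall on the sham eye. More patients would not remove the problem.

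The conclusion rests on the sequence as described (block, then sham, then laser to both eyes in one visit) and on reading 44 as patients, as the Statistical Analysis Plan states. It does not extend to ocular events, whose weakness at this sample size is low precision, nor to events between block and sham. The plan should be changed, but the primary endpoint is not in question.

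**What to change.** - Reword the objective so that the comparison is with sham-injected eyes, and limit the between-arm adverse-event comparison and its hypothesis to ocular events.
- Add an ocular analysis to the Statistical Analysis Plan: paired eyes, an exact method (McNemar on discordant pairs) and a confidence interval for the difference. State that a non-significant result will not be read as similarity.
- Report non-ocular events once per patient, as incidence after peribulbar exposure with an exact 95% confidence interval and no sham comparison. Where it was recorded, give onset relative to the block, the sham and each eye's PRP.
- The Statistical Analysis Plan is written in the past tense and already reports distribution findings. If data have been seen, disclose these changes as post hoc.

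The cost is the wording of one objective and one hypothesis, plus a short safety paragraph. No new patients or measurements are needed. The downside is that the plan gives up a between-arm claim on systemic safety, which this design could not support.

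### The secondary vital-sign hypotheses (an increase 10% lower than the sham eye's) have no absolute target, time point or rule for no rise, and no planned analysis estimates or tests them

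*Combined protocol and SAP*

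**What the plan says.** The Specific hypotheses contain three vital-sign statements of the same form:

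- Heart rate: "the post-procedure increase in heart rate will be 10% lower than the increase observed in eyes receiving a sham injection".
- Respiratory rate: "the post-procedure increase in respiratory rate will be 10% lower than the increase observed in eyes receiving a sham injection".
- Blood pressure: "the post-procedure increase in systolic and diastolic blood pressure will be 10% lower than the increase observed in eyes receiving a sham injection".

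Oxygen saturation is measured but carries no such hypothesis.

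Variables and Measurements makes the pain score primary and all the vital signs secondary. The same section schedules readings at baseline and at 1, 5, 10 and 15 minutes during PRP in each eye.

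The design is within-patient, in that "one eye of each participant was assigned to the treatment or control group according to the permutation, with the contralateral eye assigned to the corresponding" (the sentence ends by naming the other arm).

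The only sizing statement is in the Statistical Analysis Plan: "The sample size was calculated using a two-sample t-test to compare two means, based on previous results reported by" (the source is a cited trial of diclofenac for pain prevention). With alpha set at 0.05 and beta at 0.2, it concludes that "a minimum of 44 patients was required to find statistically significant differences". For analysis, the plan names the Friedman test for repeated measurements of related groups and the Mann-Whitney U test for unrelated groups, with significance at p < 0.05.

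**The concern.** The introduction presents vital signs as the objective complement to a subjective score, and the evaluator who collects that score is not masked. The vital-sign results may therefore be given real weight, so they need a question that the data can answer.

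As worded, they lack one in three respects.

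- **The target is a fraction of an unstated quantity.** Ten per cent of a 10 beats/min rise is 1 beat/min; ten per cent of a 2 breaths/min rise is 0.2. If the sham eye does not rise, a percentage reduction is undefined; if it falls, the percentage has no sensible reading.
- **The increase is not tied to a reading.** Four during-PRP readings are scheduled, and the hypotheses speak of a post-procedure increase.
- **No named analysis produces the contrast.** A significant or non-significant p-value from the listed tests would not say whether the rise was smaller in the peribulbar eye, or by how much.

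**Working it through.** **1. The plan's own figure.** The 44 cannot be reproduced, because neither the difference nor the SD is stated. It can be inverted, taking alpha 0.05 as two-sided (the plan does not say) and power 0.80, so that z₀.₉₇₅ + z₀.₈₀ = 1.960 + 0.842 = 2.802. For two independent groups of n, d = 2.802 × √(2/n):

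- n = 44 per group: d = 2.802 × √(2/44) = 0.60.
- n = 22 per group: d = 2.802 × √(2/22) = 0.84.

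Either way the source is a pain study. No vital-sign quantity enters.

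**2. What 44 pairs can detect.** Each patient gives one eye to each arm, so 44 patients are 44 pairs (11 blocks × 4 = 44 agrees). For a paired t-test with 43 degrees of freedom, the noncentral t gives 80% power at 0.432 SD of the within-patient difference in change. At assumed SDs of 5, 8 and 12 units this is 2.2, 3.5 and 5.2 units.

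**3. Power for a true 10% reduction.** The documents give no rise or SD, so both are assumptions. The target is 0.10 × rise, the noncentrality is (0.10 × rise / SD) × √44, and the pairs needed for 80% power are (2.802 × SD / target)².

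| Assumed sham rise | Target | SD of paired difference | Power, 44 pairs | Pairs for 80% |
|---|---|---|---|---|
| 5 | 0.5 | 5 | 10% | 785 |
| 5 | 0.5 | 8 | 7% | 2,010 |
| 5 | 0.5 | 12 | 6% | 4,521 |
| 10 | 1.0 | 5 | 25% | 197 |
| 10 | 1.0 | 8 | 13% | 503 |
| 10 | 1.0 | 12 | 8% | 1,131 |

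For example, rise 10 and SD 5 give noncentrality (1.0/5) × √44 = 1.33 and power 25%.

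Respiratory rate needs its own scale. With an assumed rise of 2 breaths/min the target is 0.2, and power is 14%, 10% and 7% at SD 1.5, 2 and 3.

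**4. Inputs that favour the plan.** With the same method, rise 10 and SD 3 give 58%; rise 20 and SD 5 give 74%; rise 15 and SD 3, or rise 30 and SD 6, give 90%; rise 20 and SD 3 give 99%. For 10% of the rise to equal the detectable difference, the rise must be 0.432 × SD / 0.10, which is 13 units at SD 3, 22 at SD 5 and 35 at SD 8.

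**5. If the true reduction is larger.** With a 10-unit sham rise, halving it (5 units) has power 98%, 90% and 77% at SD 8, 10 and 12.

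**6. Hypothesis against planned analysis.** The hypotheses concern a difference between two eyes of one patient in change from baseline.

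- The Friedman test ranks related measurements. It can show that readings differ over time, but gives no between-eye difference in change.
- The Mann-Whitney test is named for unrelated groups. It ignores the pairing, and the plan does not say that it would be applied to changes rather than levels.
- Neither yields an estimate with a confidence interval, and neither is set against a 10% margin.

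This step needs no assumed rise or SD.

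**The case against.** The strongest reply is that these are secondary variables. The 44 was derived for pain, and the plan never claims power for vital signs. That stands: the statement that "a minimum of 44 patients was required to find statistically significant differences" should not be read as a failed power claim for heart rate or blood pressure, and leaving secondary variables unpowered is ordinary.

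Three stronger readings are tempting and are not supported.

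- **That the target is about one unit or less, beyond what 44 pairs can resolve.** This needs a sham rise of about 10 units or less and a moderate SD. The documents give neither, and step 4 shows inputs with adequate power.
- **That the hypotheses can be neither confirmed nor refuted.** Read as at least 10% lower, a large blunting of the rise could support them, and a clearly larger rise in the peribulbar eye would count against them.
- **That chance alone would often produce an apparent 10% reduction and so a false success.** The plan has no rule that treats an observed 10% as success; its criterion is p < 0.05.

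It can also be said that no ratio of changes is planned, that a rise is a reasonable premise for a painful procedure, and that finding no rise would itself be informative. That is fair, but the plan does not say how such a result would be read.

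**Conclusion.** The point holds in a limited form. What is firm, from the text alone, is that the three hypotheses have no absolute target, no defined time point and no meaning if the sham eye does not rise, and that the listed tests neither estimate nor test the within-patient difference in change. Following the plan exactly would not answer them.

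The size of the power problem is conditional. At sham rises of 5 to 10 units and paired-difference SDs of 5 to 12, with a two-sided 0.05 paired t-test on 44 pairs, power to separate a true 10% reduction from none is about 6% to 25%. Other inputs give 74%, 90% or more. The narrow conclusion is that over much of this range the trial cannot distinguish a 10% reduction from none; it is not that the vital-sign data are uninformative. The primary pain comparison is untouched.

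**What to change.** Replace the three hypotheses with one estimand for each vital sign: the within-patient difference, peribulbar minus sham eye, in change from that eye's baseline. Use either one named time point or the mean of the 1-, 5-, 10- and 15-minute readings. Report it in beats/min, breaths/min and mmHg (systolic and diastolic separately).

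In the Statistical Analysis Plan:

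- Give a 95% CI from a paired analysis: paired t, or the Hodges-Lehmann estimate with the Wilcoxon signed-rank test if the paired differences are non-normal. The plan reports non-normal distributions within groups, but what matters here is the distribution of the differences.
- Label these analyses as estimation or exploratory, and note that 44 pairs detect about 0.43 SD of the paired difference with 80% power under a paired t-test.
- Give percentages only as description.
- Declare the change as post hoc if the data have already been analysed. Much of the Methods and analysis text is in the past tense and reports observed distributions, so this may apply.

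The cost is the wording of three hypotheses, a short addition to the analysis section and a reanalysis of readings already collected. No extra patients or measurements are needed. The downside is that the vital-sign claims become less ambitious and, if the change is post hoc, must be presented as such.
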